Improving the Frequency and Quality of Sleep Apnea Care Management

ClinicalTrials.gov Identifier: NCT01916655

July 25, 2019

BACKGROUND:

Obstructive sleep apnea (OSA) is highly prevalent in the Veteran population given the risk factors of male gender, being overweight, and increasing age. OSA is caused by upper airway obstruction, resulting in arousals from sleep and hypoxia. While continuous positive airway pressure (CPAP) is a highly efficacious treatment for OSA, adherence with treatment is suboptimal. Because research is clear that adherence patterns are established early in treatment, we evaluated an mHealth intervention to facilitate early, productive interactions between patient and provider that improve the quality of care and ultimately improve adherence with therapy and outcomes. The mHealth interventional approach can allow for improved, more timely delivery of our Sleep Apnea Self-Management Program (SM).

OBJECTIVES:

The objective of this proposal was to evaluate an mHealth system for patients with Obstructive Sleep Apnea syndrome (OSA) that facilitates patient-centered, collaborative management for patients who are prescribed the gold-standard treatment, continuous positive airway pressure (CPAP).

DESIGN & METHODS:

The evaluative aspect of this proposal is designed as a randomized clinical trial-- Usual Care (Usual Care (control; UC); Self-Management Care (intervention 1; SM); and Self-Management via mHealth (intervention 2; SM-Mobile). The key feature of the SM-Mobile intervention is the use of a system that allows for receiving the SM via website at their convenience. The provider is able provide more directed feedback to the patient based on the telemedicine interaction, and the patient benefits from timely contact with the provider. Specific inclusion and exclusion criteria included: age > 18 years; confirmed diagnosis of moderate-severe OSA; being newly prescribed CPAP therapy; having chronic symptoms as noted on screening symptom checklist; and fluency in English. Patients were recruited from the VA San Diego Healthcare System Sleep Clinic. Participants were enrolled for a 4-month time period.

FINDING:

Overall Sample: The overall sample was aged 53.1 ± 13.6 , had a body mass index (BMI) of 32.6 ± 5.7 , apnea-hypopnea index (AHI) of 30.3 ± 18.9 , and a baseline Epworth Sleepiness Score (ESS) of 11.8 ± 5.3 . 90% of the sample were men. There were no significant differences between the groups on BMI, AHI, ESS, sleep apnea symptoms, insomnia symptoms or depressive symptoms.

Aim 1: To examine the effect of the Self-Management Care delivered by mHealth (SM-Mobile) intervention compared to Usual Care (UC) and Self-Management Care (SM) on level of CPAP adherence relative to Usual Care. The three groups were compared to see if there were differences on adherence. No statistically significant differences were found between UC, SM and SM-Mobile groups at the 2-month timepoint (4.0 ± 2.2 , 3.9 ± 2.4 , and 3.8 ± 2.4 hours per night, respectively; $F = .113$; $p = .893$). or the 4-month timepoint (3.6 ± 2.2 , 3.6 ± 2.5 , and 3.6 ± 2.5 hours per night, respectively; $F = .041$; $p = .959$).

In addition, we had CPAP efficacy metrics, including the residual Apnea-Hypopnea Index (AHI) and mask leak. At the 4-month time point, CPAP resulted in very good control of sleep apnea as evidenced by the mean AHI of 3.3 across the entire group. There were no group differences on residual AHI (UC, SM, and SM-Mobile of 3.0, 3.6 and 3.3, respectively). The same was true at the 2-month timepoint (mean residual AHI = 3.4; 3.2, 3.7 and 3.5, respectively). Mask leak was also well within normal limits at both the 2-month (mean = .14; .11, .15, and .16 lps) and 4-month timepoints (mean = 12; .12, .12, and .13 lps).

Aim 2: To examine the effect of the SM-Mobile intervention, compared to Usual Care and Self-Management Care, on the patient's experience of the quality of patient-centered, collaborative care (as measured by the Patient Assessment of Chronic Illness Care [PACIC]). The PACIC results in a total score and five subscale scores (Patient Activation, Delivery/support, Goal, Problem-solving, and Follow-up). The three intervention groups did not differ statistically (UC, SM, SM-Mobile) (3.3 ± 1.1 ; 3.4 ± 1.1 ; 3.4 ± 1.1 , respectively) on the PACIC Total Score. Higher scores indicated higher ratings of chronic illness care. The range of scores for the subscales was 2.6 to 3.7, with the higher overall scores on the Delivery/support subscale and the lowest on the Follow-up subscale. Overall, the scores were as high or higher than those reported in the literature for patients with similar chronic medical conditions, such as diabetes, asthma, depression and arthritis, indicating that the interventions studied in this project resulted in higher than average chronic illness care, as rated by patients.

Aim 3: To examine the effect of SM-Mobile, compared to UC and SM, on OSA apnea outcomes (e.g., OSA symptoms and OSA-specific health-related quality of life [HRQOL]). The Epworth Sleepiness Scale scores dropped from baseline to 2-months by 3.4 points and to 4-months by 4.0 points. Given that the cut-off for the ESS is 10 points (above which is considered sleepy; below which is considered within normal limits), all three interventions combined to reduce the sleepiness level of the sample from the sleepy range to the normal limits range (i.e., from mean ESS score of 11.8 to mean ESS score of 8.4 and 7.8 for 2-months and 4-months respectively). The mean ESS scores did not differ significantly between the groups at either the 2-month timepoint (8.3, 8.5, and 8.5 for the 3 groups respectively, UC, SM and SM-Mobile) or the 4-month timepoint (7.9, 7.4, and 8.2 for the 3 groups respectively, UC, SM and SM-Mobile). Sleep quality as measured by the Pittsburgh Sleep Quality Index was also significantly improved across all 3 groups from baseline (mean 11.9) to 2-months (2.8 points, mean 9.1) and to 4-months (2.9 points, mean 9.0). The mean PSQI scores did not differ significantly between the groups at either the 2-month timepoint (8.7, 9.4, and 9.5 for the 3 groups respectively, UC, SM and SM-Mobile) or the 4-month timepoint (8.5, 9.0, and 9.7 for the 3 groups respectively, UC, SM and SM-Mobile).

STATISTICAL ANALYSIS PLAN (SAP):

Data Analytic Plan. Preliminary analyses will begin with an examination of the distribution of variables to assess their characteristics (means, standard deviations, skewness, and kurtosis), to provide descriptive statistics of the study population, and to allow assessment of randomization. Continuous measures will be tested for normality and homogeneity of variance. Non-normally distributed variables will be transformed to meet the normal distribution assumption for linear statistical models.

The research question in the primary aim 1 will be addressed by comparing the CPAP adherence at post-intervention among the three intervention groups (UC, SM, SM-Mobile) and secondary aims 2 and 3 will be addressed by comparing the three intervention groups (UC, SM, SM-Mobile) on the changes in PACIC, OSA symptoms and OSA HRQOL from pre-intervention to post-intervention. The analytic model is based on an analysis of variance on the post-intervention measure (primary aim) or the change measures (secondary aims). For the change measures, the ANOVA will be accompanied by an analysis of covariance (ANCOVA) on the change scores with intervention as a main effect and the corresponding baseline measurement (baseline PACIC, OSA symptoms and OSA HRQOL) as the covariate. Adjustments will be made to correct for other baseline imbalances between groups, and to adjust for variables known to influence outcome independently of intervention. To explore this, univariate methods will be used. Each of the following variables will be assessed for imbalance between the three intervention groups and their association with each of the outcomes using a univariate analysis (ANOVA, Fisher's exact test or Spearman correlation coefficient as appropriate): age, gender, education and baseline OSA

severity. These variables will be included as covariates in the ANCOVA model if found to be moderately associated ($p < 0.15$) with the outcome under study (CPAP adherence, CAHPS, PACIC, OSA symptoms and OSA HRQOL) or unbalanced ($p < 0.10$) among intervention groups. The outcomes in secondary aims 2 and 3 will also be assessed by the random effects model, which is useful for examining changes in variables from clustered or longitudinal data and allows us to account for all levels of clustering when analyzing the data. It accommodates unequal time intervals and will include all available data, minimizing the effects of missing data on the analyses. The data analytic plan for secondary aim 4, which involves a cost analysis among three interventions [and a calculation of the adherence level per intervention cost], is fully described in section D.7 below. An intent-to-treat analysis will be performed and no correction will be made for multiple comparisons. All above analyses will be performed in R.¹¹⁰ Given below are detailed analysis plans for the primary aim and secondary aims 1 and 2.

Aim 1: An ANOVA will be used to assess the CPAP adherence at post-intervention among the three groups. Followed will be an ANCOVA by including potential covariates. Any variable that is significantly different at baseline ($p < 0.10$) and found to be associated with response ($p < 0.15$) as well as any clinically significant variables will be included as covariates.

Aim 2: An ANOVA will be used to assess the post vs. pre changes in PACIC among the three groups. An ANCOVA will be performed with treatment as a main effect and baseline score as a covariate. Any variable that is significantly different at baseline ($p < 0.10$) and found to be associated with response ($p < 0.15$) as well as any clinically significant variables will be included as covariates. As a secondary analysis, the change in PACIC will also be evaluated using a random effects model with a group, time and a group-by-time interaction term.

Aim 3: An ANOVA will be used to assess the post vs. pre changes in OSA symptoms and OSA HRQOL among the three groups. An ANCOVA will be performed with treatment as a main effect and baseline score as a covariate. Any variable that is significantly different at baseline ($p < 0.10$) and found to be associated with response ($p < 0.15$) as well as any clinically significant variables will be included as covariates. As a secondary analysis, a random effects model with a group-by-visit interaction term will be used to assess the rate of change in PACIC differs among three intervention groups.

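### The Aim 2 conclusion credits the interventions with better-than-average care, but the randomised comparison shows no significant PACIC difference and no comparator scores are given

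*Combined protocol and SAP*

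**What the plan says.** Under FINDING, Aim 2 is stated as a comparison between randomised arms: "To examine the effect of the SM-Mobile intervention, compared to Usual Care and Self-Management Care". The reported scores are "3.3 ± 1.1 ; 3.4 ± 1.1 ; 3.4 ± 1.1 , respectively) on the PACIC Total Score", in the order UC, SM, SM-Mobile, and the three arms are said not to differ significantly. No F, p, confidence interval or sample size is given for PACIC, and neither baseline scores nor changes are shown.

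The paragraph then turns to an outside comparison: "Overall, the scores were as high or higher than those reported in the literature for patients with similar chronic medical conditions". It names diabetes, asthma, depression and arthritis as examples, gives no score for any of them, and draws its conclusion from this: "indicating that the interventions studied in this project resulted in higher than average chronic illness care, as rated by patients".

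DESIGN & METHODS labels UC as the control, SM as intervention 1 and SM-Mobile as intervention 2. The results and the SAP nevertheless count all three as intervention groups. For PACIC, the SAP (Data Analytic Plan and Aim 2) plans an ANOVA on pre-to-post change, an ANCOVA with the baseline score as covariate, and a random effects model. All of these compare the three arms; none uses external norms.

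**The concern.** The closing sentence of Aim 2 is causal, but it does not come from the comparison that can support a causal statement. Randomisation allows SM and SM-Mobile to be compared with UC. It says nothing about how this clinic's patients compare with patients who have other diseases, in other settings, surveyed at other times.

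A reader who takes that sentence as the result would believe that the study interventions improved patient-rated care. The trial's randomised comparison does not show this, and a level found in all arms, control included, cannot be attributed to SM or SM-Mobile.

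The same habit appears, less strongly, under Aim 3. There a pooled fall in Epworth Sleepiness Scale (ESS) score is credited to the three interventions jointly, although every participant entered on "being newly prescribed CPAP therapy" and the arms did not differ significantly.

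This is a fault of interpretation in the results summary, not in the planned analysis.

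**Working it through.** **1. Is the reported non-significance consistent with the scores?** Inputs are the PACIC means 3.3, 3.4 and 3.4 and SD 1.1 (FINDING, Aim 2). The variance of the three means is 0.003333. For n per arm, F = n × 0.003333 / 1.1².
- n = 30 (assumed): F = 0.083, p = 0.92.
- n = 200 (assumed): F = 0.551, p = 0.58.
- Most unfavourable rounding (means 3.25, 3.45, 3.45; SD 1.05): p = 0.70 at n = 30 and 0.09 at n = 200.

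The null statement therefore agrees with the printed figures over this range.

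**2. How large are the contrasts that Aim 2 asks for?**
- SM-Mobile minus UC: 3.4 - 3.3 = 0.1. Rounding limits are 3.35 - 3.35 = 0.0 and 3.45 - 3.25 = 0.2. In SD units, 0.1 / 1.1 = 0.09.
- SM-Mobile minus SM: 3.4 - 3.4 = 0.0, with rounding limits -0.1 to 0.1.

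**3. What range of n is plausible?** None is stated. A rough range comes from the Aim 1 adherence results, assuming a one-way ANOVA on untransformed hours with equal arms: n = F × mean(SD²) / var(means).
- 2 months (means 4.0, 3.9, 3.8; SDs 2.2, 2.4, 2.4; F = 0.113): 0.113 × 5.453 / 0.0100 = 61.6.
- 2 months, lower rounding limit (means 4.05, 3.95, 3.75; SDs 2.15, 2.35, 2.35): 0.1125 × 5.2225 / 0.02333 = 25.2.
- 2 months, upper rounding limit (means 3.95, 3.90, 3.85; SDs 2.25, 2.45, 2.45): 0.1135 × 5.689 / 0.0025 = 258.3.
- 4 months (all means print as 3.6; F = 0.041): the largest possible variance of the means is 0.003333 (3.55, 3.55, 3.65), so n is at least 0.0405 × 5.5425 / 0.003333 = 67.3, that is 68.

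If the same number contributed at both visits, this gives roughly 68 to 258 per arm.

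**4. What would the PACIC interval look like?** Assuming the same n for PACIC, the half-width is t(0.975, 3n - 3) × 1.1 × √(2/n). The intervals are unadjusted, in line with the SAP's decision not to correct for multiple comparisons.

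| n per arm | Half-width | SM-Mobile minus UC, 95% CI |
|---|---|---|
| 30 (assumed low return) | 0.565 | -0.46 to 0.66 |
| 68 | 0.372 | -0.27 to 0.47 |
| 258 | 0.190 | -0.09 to 0.29 |

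Rounding of the means can shift each interval by up to 0.1. The planned measure is change, whose SD is not given, so these intervals are illustrative only.

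**5. Can the literature comparison be checked?** No. There is no comparator score, SD, sample size or test. Its logic also falls short: scores equal to or above published ones do not establish scores above average.

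**6. ESS (secondary point).** The pooled mean fell by 11.8 - 7.8 = 4.0 at 4 months. Baseline means by arm are not shown.
- UC baseline equal to the pooled 11.8: UC fell by 11.8 - 7.9 = 3.9.
- UC baseline between 10.8 and 12.8 (assumed): UC fell by 2.9 to 4.9.

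UC's means of 8.3 and 7.9 lie below the 10-point cut-off at both visits.

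**The case against.** The strongest defence is that nothing is hidden. The null result and all three scores come earlier in the same paragraph. Since the document counts UC as an intervention group, the sentence can be read as describing care in the whole study rather than superiority over control. On that view it is one over-worded sentence on a secondary aim, with no bearing on design, endpoint or test.

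Part of this stands. The matter is one of wording, the trial's own scores are shown, and whether the published scores are in fact lower cannot be judged from the document. But printing the null first does not license a causal claim after it. If UC is included among the interventions, the sentence describes a level of care and has no contrast from which to infer an effect.

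A second objection is that the inferred sample sizes are fragile, and this is fair. With unequal arms the 4-month F is reachable at a total of about 174, or 174 / 3 = 58 per arm. The printed p of 0.959 moves the equal-arm bound from 68 to 69. The SAP also allows transformation of non-normal variables, which would invalidate the back-calculation. None of this touches the conclusion, which needs only the 0.1-point difference and the absence of comparator scores.

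On ESS, the summary does say that the groups had no significant baseline difference on that scale. This makes a UC baseline near 11.8 plausible, but does not show it.

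**Conclusion.** The concern holds. The causal conclusion on patient-rated care is unsupported as written. It draws on an unplanned comparison across diseases with no comparator figures, while the randomised comparison shows 0.1 point (0.0 to 0.2 with rounding; 0.09 SD) between SM-Mobile and UC, and 0.0 (-0.1 to 0.1) between SM-Mobile and SM.

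This is not proof of no effect. Under the stated assumptions on n, equal arms and raw scores, the SM-Mobile versus UC interval includes zero and differences in both directions. The supportable statement is that no significant difference was found, with the intervals showing what remains possible.

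The ESS sentence has the same weakness to a lesser degree, and its arithmetic depends on an assumed UC baseline. The correction should be made because it changes a stated conclusion. It does not call the design or the planned analysis into question.

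**What to change.** - **Aim 2 conclusion:** replace the closing sentence with the randomised result, namely no statistically significant difference in patient-rated care among UC, SM and SM-Mobile.
- **Supporting estimates:** report SM-Mobile minus UC and SM-Mobile minus SM, each with a 95% CI, from the baseline-adjusted PACIC ANCOVA already in the SAP. State the number analysed per arm.
- **Literature comparison:** either delete it, or show the scores and their source and call it descriptive of all arms, usual care included.
- **Aim 3 ESS sentence:** describe a fall after starting CPAP, seen in all three arms, that a pooled before-and-after comparison cannot attribute to the study interventions.

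The cost is two reworded sentences, two contrasts from an analysis already planned, and a less favourable summary. No new data are needed. If the literature comparison stays, its figures and source must be added.

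### Aim 3 is only partly answered: no OSA HRQOL result, no planned between-arm change analysis, and a SAP random effects model for Aim 3 that names the wrong outcome

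*Combined protocol and SAP*

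**What the plan says.** The Finding section poses Aim 3 as the effect of SM-Mobile, against UC and SM, "on OSA apnea outcomes (e.g., OSA symptoms and OSA-specific health-related quality of life [HRQOL" (the bracket closes directly after).

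The SAP is more definite. Its Data Analytic Plan says that secondary aims 2 and 3 compare the three arms "on the changes in PACIC, OSA symptoms and OSA HRQOL from pre-intervention to post-intervention", and it lists the outcomes under study as "CPAP adherence, CAHPS, PACIC, OSA symptoms and OSA HRQOL". The SAP paragraph for Aim 3 states: "An ANOVA will be used to assess the post vs. pre changes in OSA symptoms and OSA HRQOL among the three groups". An ANCOVA with the baseline score as covariate follows. That paragraph closes with a random effects model that "will be used to assess the rate of change in PACIC differs among three intervention groups".

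The Aim 3 results cover two instruments:

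- **ESS.** "The Epworth Sleepiness Scale scores dropped from baseline to 2-months by 3.4 points and to 4-months by 4.0 points". On the arms, "The mean ESS scores did not differ significantly between the groups at either the 2-month timepoint" or at 4 months.
- **PSQI.** "Sleep quality as measured by the Pittsburgh Sleep Quality Index was also significantly improved across all 3 groups from baseline", followed by arm means at both visits, again described as not significantly different.

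**The concern.** Aim 3 asks whether SM-Mobile changes OSA symptoms and OSA-specific quality of life relative to two comparators. A reader of the results cannot find the quality-of-life answer. For the instruments that are shown, the reader cannot find the planned estimate, which is the difference between arms in change from baseline. The only positive significance claim is a before-and-after statement on the pooled sample. All three arms consist of patients newly prescribed CPAP, so a pooled improvement is expected whether or not the self-management programmes add anything.

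The SAP has a related fault. Read literally, its Aim 3 paragraph fits the longitudinal model to PACIC, which already has its own model under Aim 2. An analyst following that paragraph would fit no longitudinal model to either Aim 3 outcome.

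**Working it through.** **1. Planned against reported**

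| Item | SAP | Finding section |
|---|---|---|
| OSA HRQOL | Change by arm, ANOVA and ANCOVA | No score, test or explanation |
| OSA symptoms | Change by arm, ANOVA and ANCOVA | ESS: pooled drop and arm means by visit. The separately listed sleep apnea symptoms: baseline comparison only |
| PSQI | Not named | Pooled drop, arm means by visit |
| Longitudinal model, Aim 3 | Data Analytic Plan: applies to outcomes of aims 2 and 3. Aim 3 paragraph: PACIC | None reported |

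OSA HRQOL occurs four times in the SAP: as a change outcome, as a baseline covariate, in the list of outcomes under study, and in the Aim 3 paragraph. In the Finding section it occurs only in the statement of the aim.

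The Overall Sample paragraph lists ESS and sleep apnea symptoms as separate baseline variables. This suggests a symptom measure distinct from ESS, and no follow-up value is given for it.

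**2. The reported figures agree with each other**

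- PSQI: 11.9 − 2.8 = 9.1 and 11.9 − 2.9 = 9.0, as stated. Unweighted arm averages: (8.7 + 9.4 + 9.5)/3 = 9.20 and (8.5 + 9.0 + 9.7)/3 = 9.07. The small gaps are compatible with rounding and unequal arm sizes.
- ESS: 11.8 − 3.4 = 8.4 and 11.8 − 4.0 = 7.8, as stated. Unweighted arm averages: (8.3 + 8.5 + 8.5)/3 = 8.43 and (7.9 + 7.4 + 8.2)/3 = 7.83.

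The arithmetic is sound; the problem lies in what is missing. Neither instrument has a baseline mean by arm, so change by arm cannot be derived.

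**3. What the PSQI significance statement can carry**

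The documents give no sample size, SD of change, test or p value. I therefore assumed an SD of change of 3 to 5 points and a total N of 30 to 300, and used a paired t-test on the 4-month drop, t = 2.9/(SD/√N):

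- SD 5, N 30: t = 3.18, p = 0.0035 (least favourable corner).
- SD 4, N 60: t = 5.62, p < 0.001.
- SD 3, N 300: t = 16.74, p far below 0.001.

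The smallest N giving p < 0.05 is 7, 10 and 14 for SD 3, 4 and 5. Pre-post significance is therefore plausible throughout the assumed range. It is also uninformative about the aim, because the calculation contains no comparison between arms.

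**The case against.** **The symptom half is addressed, and PSQI is extra.** ESS is reported first, at both visits and by arm, and it bears on symptoms. PSQI is introduced as a further result and described as sleep quality. The wording of the aim offers its outcomes as examples. This stands to a degree: Aim 3 is partly answered, not unanswered. The latitude of an example list does not reach the SAP, which names OSA symptoms and OSA HRQOL outright.

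**A reader might infer that PSQI was put in the place of HRQOL, or that reporting was selective.** The documents do not support that. The SAP names no instrument for either domain, so ESS is as absent from it as PSQI. The SAP text also refers to a section D.7 that is not in the document, so measures may be listed elsewhere. The null comparison between arms on PSQI is disclosed with all six means, and no benefit of SM-Mobile is claimed from it.

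**A reader might also take the 4-month PSQI means, 9.7 in SM-Mobile and 8.5 in UC, as a sign of harm.** That does not follow. There is no SD, N or baseline by arm, and the document reports the three-arm comparison as non-significant. With equal arms of 20 to 100 and an assumed SD of 3 to 5, the F-test p value for these means runs from 0.749 down to 0.019, so they cannot be read as an effect.

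**The pre-post test may come from a planned model.** The random effects model would ordinarily yield a time effect, so the test cannot be called outside the plan. What stands is that it is unidentified and does not compare arms.

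**The PACIC sentence looks like a copying slip.** Probably so, since the Data Analytic Plan states the intended scope. But it is an analysis rule that is wrong as written.

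**Conclusion.** The point holds as incomplete reporting of a secondary aim, together with one internal contradiction in the SAP. Of the two outcome domains named for Aim 3, OSA HRQOL has no result in any of three arms at either follow-up visit. OSA symptoms are represented by ESS at most, with no follow-up for the separately listed symptom variable. Neither domain has the planned between-arm analysis of change.

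The prespecified status of ESS and PSQI cannot be determined from these documents. The pooled PSQI improvement is probably real as a before-and-after change, on the assumed SD and N above, but it is not evidence about SM-Mobile.

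The reading of the baseline list as showing a symptom measure distinct from ESS is an inference from ESS and sleep apnea symptoms being listed separately. No conclusion about motive or about the direction of the missing HRQOL result is warranted.

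**What to change.** 1. Report change in OSA HRQOL and in OSA symptoms by arm: ANCOVA adjusted for the baseline score, SM-Mobile minus UC and SM-Mobile minus SM, each with a 95% CI and the number analysed. If HRQOL is unavailable, say why. Name the instrument for each domain.
2. In the random effects sentence of the SAP's Aim 3 paragraph, replace PACIC with OSA symptoms and OSA HRQOL, so that it agrees with the Data Analytic Plan.
3. Label whole-sample pre-post changes in ESS and PSQI as descriptive and not evidence of an intervention effect. Identify the test behind the PSQI statement, and state whether PSQI was prespecified or additional.

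The cost is a one-line SAP correction, some labelling, and analyses that the plan already calls for, provided the data were collected. CAHPS, which is listed among the outcomes under study but has no aim, analysis or result, is a separate minor point that can be tidied in the same edit.

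### Does the unspecified rule to transform non-normal variables leave the primary CPAP adherence test unsound?

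*Combined protocol and SAP*

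**What the plan says.** The preliminary-analysis paragraph of the SAP (Data Analytic Plan) lists means, standard deviations, skewness and kurtosis as descriptive checks. It then says "Continuous measures will be tested for normality and homogeneity of variance" and continues with "Non-normally distributed variables will be transformed to meet the normal distribution assumption for linear statistical models". No test, significance level, transformation, offset for zeros, back-transformation or fallback is given.

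For the primary aim, the SAP's Aim 1 paragraph says "An ANOVA will be used to assess the CPAP adherence at post-intervention among the three groups". Neither that paragraph nor the general description of the analytic model gives a unit or scale for adherence, or exempts it from the rule. The secondary aims use change scores.

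The Findings section (Aim 1) gives adherence in hours: "4.0 ± 2.2 , 3.9 ± 2.4 , and 3.8 ± 2.4 hours per night, respectively" at 2 months and "3.6 ± 2.2 , 3.6 ± 2.5 , and 3.6 ± 2.5 hours per night" at 4 months, with F and p values. It mentions no transformation.

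**The concern.** The rule is worded as an instruction, and it looks at variables, whereas a linear model is concerned with residuals or estimates. CPAP hours cannot fall below zero, so a normality test could well fail and trigger the rule for the primary outcome. The analyst would then choose the scale of the primary test after seeing the data, and the plan makes no multiplicity correction that would limit such a choice.

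Three consequences are possible.

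- A test on a log or root scale no longer compares mean hours per night, the quantity reported. Arms with equal means can differ on another scale.
- If some participants never use the device, any monotone transformation leaves them as a cluster, so the rule could miss its own aim and still change power.
- For the change scores of Aims 2 and 3, plain log, root and Box-Cox transformations are undefined at negative values.

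**Working it through.** **1. The reported tests.** With 2 numerator degrees of freedom and d = N − 3, the upper tail of F is p = (1 + 2F/d)^(−d/2). N is not stated, so it was varied from 60 to 600.

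- F = .113 gives p = .8932 to .8934; the Findings state .893.
- F = .041 gives p = .9598 to .9599; rounding of F allows .9594 to .9603, so the stated .959 is compatible.

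**2. Arm size.** Assume equal arms and an unadjusted ANOVA on raw hours. Then n per arm = F × mean(SD²) / variance of the arm means.

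- 2 months: mean(SD²) = (2.2² + 2.4² + 2.4²)/3 = (4.84 + 5.76 + 5.76)/3 = 5.45. The variance of 4.0, 3.9 and 3.8 is 0.01. So n = 0.113 × 5.45 / 0.01 = 62, with a range of 25 to 258 once rounding is allowed for.
- 4 months: all three means round to 3.6, so they lie within 3.55–3.65, and n is at least about 67.

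The main simulations use 70 per arm.

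**3. Could the rule be triggered?** A normal distribution with mean m and SD s has a share Φ(−m/s) below zero. For 4.0/2.2 this is Φ(−1.82) = 3.5%; for 3.6/2.5 it is Φ(−1.44) = 7.5%. Exact normality is therefore impossible. Whether a test detects this depends on the test and on N. In simulation (mean 3.65, SD 2.4, 0–20% zeros, users drawn from a normal truncated to 0–12 h):

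| Check on raw hours | Trials failing |
|---|---|
| Shapiro, pooled residuals, 70 per arm | 99.8–100% |
| Shapiro, pooled residuals, 30 per arm | 59–94% |
| D'Agostino | 68–100% |

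With an illustrative limit of 1 on absolute skewness and excess kurtosis, raw hours would pass in 80–100% of trials.

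**4. Type I error.** Raw-scale ANOVA rejects in 4.8–5.1% of null trials at 30 and 70 per arm. A second simulation, with a different shape for users' hours and 50 or 80 per arm, gives 3.9–5.8% across raw, square root, log(x+1) and log(x+0.01). When the scale is chosen on pooled data without group labels, the two simulations give 4.5–5.1% and 4.5–5.8%. Only picking the smallest p across scales after seeing group results raises it clearly: 6.4–7.5% over three scales, 7.3–8.2% over four.

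**5. Power, one arm improved by 1 h among users, 70 per arm.** The last column shows which scale is chosen when the aim is the best Shapiro fit, blind to group.

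| Zeros | Raw | log(x+1) | sqrt | Scale chosen |
|---|---|---|---|---|
| 0% | 72 | 86 | 83 | sqrt in 99% |
| 7% | 63 | 55 | 52 | raw in 91% |
| 14% | 55 | 34 | 33 | raw in 100% |
| 20% | 48 | 21 | 22 | raw in 100% |

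Skewness explains the last column. At 7, 14 and 20% zeros, raw skewness is +0.39, +0.12 and −0.15; log(x+1) moves it to −0.73, −0.89 and −0.93, and the square root is similar. The transformations that cost power are those that take the data further from normal, against the rule's stated purpose.

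**6. What fixing raw hours would cost.** Raw against log(x+1) power is 76% v 88% when zeros fall from 14% to 2% with +0.5 h, and 72% v 86% with no zeros and +1.0 h. In another no-zeros case, where users under 3 h gain 2 h, raw power is 73% against 98% after transformation. A Kruskal-Wallis sensitivity test gives 69% and 73% in the first two cases, so it does not reliably recover the difference.

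**The case for a change.** The strongest case for acting is that the SAP sets numerical thresholds elsewhere (p < 0.10 and p < 0.15 for covariates), so their absence here is a genuine omission, and a reader who follows the wording literally could transform even when it does not help. A transformed test also answers a different question. With equal means of 3.6 h, the reported SDs and zeros ranging from none to 2/14/14% by arm, raw hours reject in 4.6–5.3% of trials, log(x+1) in 6.0–8.0% and the square root in 5.5–8.9%. Raw-scale ANOVA is valid without the rule, and the remedy would be a few words.

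Much of this stands. The test, cut-off, transformation and scale are unspecified, and stating hours per night would be tidier. Three parts carry less weight.

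- A trigger does exist, namely the normality test; only its form is missing.
- The documents give no count of zero-hour users. The means and SDs are compatible with such a cluster but do not show one.
- The difficulty with negative change scores assumes that the differences themselves are transformed. Scores could be transformed before differencing, and signed-value transformations exist.

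The literal reading would also mean transforming in order to reach normality and then keeping a scale further from it. That is not a sensible execution of a rule whose purpose is stated in the same sentence.

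**Conclusion.** No change is called for. The plan leaves out a detail that an analyst would fill sensibly. Done blind to group and in line with the rule's purpose, that choice holds type I error at about 4–6%. It also keeps raw hours in 90–100% of trials in the settings where transformation would cost power. The Findings report untransformed means and SDs in hours per night, with p = .893 and .959, and nothing shows that the rule was invoked or altered a result.

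Imposing original scales on every outcome gives up 12 to 25 percentage points of power in some plausible settings (88 − 76 = 12; 98 − 73 = 25) and gains power in others, so it is a trade-off. Naming a transformation and its trigger would add detail without making a sensible analysis any sounder.

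The conclusion rests on assumed arm sizes, shapes of use and zero shares, because the documents give none of these. It also assumes that the scale is not picked by comparing p values between groups; if it were, the error rate would be about 6–8%. No simulation was run for PACIC, OSA symptoms or HRQOL, so for those outcomes the conclusion rests on reasoning alone.
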